1.3 INCLUSION AND EXCLUSION CRITERIA

1.3.1 Inclusion Criteria

Subjects will be eligible to participate in the study if **all** of the following conditions exist:

1. Subjects must be 18 years old or older.
2. Subject or legally authorized representative must be able to understand and sign an IRB/IEC approved informed consent form (ICF).
3. Subject must have had bilateral implantation of AcrySof PanOptix or AcrySof PanOptix Toric models for 3 years to 5 years prior to enrolment, including implantation up to 90 days before the 3-year timepoint and up to 90 days after the 5-year timepoint. A subject may have a Toric lens in one eye and a non-Toric in the fellow eye.
4. Subject must have a documented medical history and required preoperative and operative information available for retrospective data collection.

1.3.2 Exclusion Criteria

Subjects will be excluded from participation in the study if any of the following conditions exist:

1. Subject is currently participating in another investigational drug or device study.
2. Subject has had corneal refractive surgery after of AcrySof PanOptix or AcrySof PanOptix Toric IOL implantation.
3. Subject exposed to a study IOL for a minimum of 3 years (-90 days) prior to Visit 1 that have subsequently undergone an IOL exchange and are no longer implanted with a study IOL at the time of enrollment.
4. Subject is pregnant or nursing at the time of enrollment.
5. Childbirth after IOL implantation.
6. Subject's retrospective data were not properly documented

1.3.3 Exit/Discontinuation Criteria

Subjects will exit the study if **any** of the following conditions exist:

1. Subject voluntarily withdraws from the study.
2. Subject death.
3. Subject completes the protocol.
4. Subject is non-compliant with the protocol
5. Subject's well-being, in the opinion of the Investigator, would be compromised by study continuation.

1.4 RANDOMIZATION

Not applicable.

1.5 MASKING

This is an open-label study.

1.6 INTERIM ANALYSIS

There are no interim analyses planned for this study.

1.7 FINAL ANALYSIS

Database lock will occur no later than 5 weeks following the last subject enrolled (targeting a number of 200 enrolled subjects). A detailed description of the planned final effectiveness and safety analyses are in Section 5 and Section 6, respectively.

2 ANALYSIS SETS

2.1 SUBJECT POPULATION(S) FOR ANALYSIS

Subject populations for analysis include:

The FAS population will be the primary population for all safety analyses and effectiveness analyses include all eyes of enrolled subjects who pass the screening criteria and had non-key ICF PDs noted in the PDCF.

3 ANALYSIS STRATEGY

3.1 STUDY SUMMARIES FOR TABLES AND LISTINGS

All summary statistics will be based on the type of variable. For categorical variables (e.g., sex, race), the number and percentage of eyes within each category of interest will be presented. For continuous variables (e.g., age, VA), number of subjects with non-missing data, mean, median, standard deviation, minimum and maximum, and two-sided 95% confidence interval (CI) for the mean, when applicable, will be reported. Tables will be presented by subjects or eyes as applicable. All data listings will include the following subject characteristics: age and sex. Age, race, ethnicity, and sex are required fields; as such, there should be no missing data for these variables across tables and listings, when presented.

3.2 PRESENTATION OF TABLES AND LISTINGS

In general, tables will be stratified by model (toric and non-toric). Subjects implanted with a toric lens in one eye and a non-toric in the other will be assigned as toric in the subject level tables. Eye-

level tables will be further stratified by first eye and second eye (if applicable), separately, and by all eyes. For subjects bilaterally implanted on the same day, OD is assigned as first eye, and OS is assigned as second eye.

Listings will be organized by lens model and will be sorted by 1/ IOL type (toric/non-toric), 2/ model number, and 3/subject ID. In tables where visit data are presented, only scheduled visits are included.

4 SUBJECT CHARACTERISTICS AND STUDY CONDUCT SAMPLES

Subject characteristics and study conduct summaries include tables and/or listings such as a subject disposition table, demographics, baseline characteristics tables (including age, sex, race, ethnicity, keratometry, biometry), summary of subjects by site, and a listing of screen failures by reason. Retrospectively collected preoperative baseline characteristics will include surgical report data, such as lens power and IOL calculation method, biometry (axial length, Anterior Chamber Depth [ACD], as well as white-to-white and lens thickness if available), keratometry (corneal cylinder [K2(D) – K1(D)]), and preoperative manifest refraction spherical equivalent (MRSE) and preoperative predicted residual refractive error (PRRE) (cylinder and spherical equivalent). Further details are provided in the section below.

Unless otherwise stated, the analysis population for analyses in Section 4 is the FAS, as defined in Section 2.1.

4.1 SUBJECT DISPOSITION

A subject disposition table that displays the number of all enrolled subjects, the number of subjects who completed the study, the number of subjects discontinued, and premature study discontinuation reasons for each subject, including screen failures, who discontinued the study will be presented. Two additional tables will be output – one table that displays the number and percentage of subjects enrolled and their completion status (e.g., completed, discontinued) by site and one table that displays the number and percentage of enrolled eyes for each study device and model number by first eye, second eye (if applicable), and all eyes.

A listing of screen failures will be provided and will include subject ID, age, sex, lens model, and inclusion/exclusion criteria for subjects that failed. A listing of patients who discontinue or end the study treatment prematurely will also be output and includes subject ID, age, sex, study device, lens model (lens model OD/lens model OS), discontinuation date, discontinuation reason, and if other reason, specify. Lastly, protocol deviations will be presented in a listing and will include subject ID, age, sex, study device, lens model, deviation date, deviation severity (key/non-key), deviation type and sub-type (e.g., procedures and tests, ICF issues, inclusion/exclusion), protocol deviation comment, action taken, and whether the PD resulted in exclusion from the FAS.

4.2 DEMOGRAPHIC AND BACKGROUND CHARACTERISTICS

The demographic and background characteristics listed below will be summarized by the number and percentage of subjects for categorical variables and descriptive statistics for continuous variables (n, mean, standard deviation, median, minimum and maximum). Surgical report data will be presented in a separate table for all eyes by toricity.

Demographics at Visit 1 (subject-level)

Categorical variables

- Age (<65 years, ≥65 years)
- Sex (Female, Male, Unknown, Undifferentiated)
- Race (per CRF, plus “Multiple” if a patient has more than one race identified in the CRF)
- Ethnicity (per CRF)

Continuous variable

- Age (years)

Surgical Report (eye-level)

- Lens power (as a continuous variable, reporting only n, median, min, and max)
- Whether surgical reason was due to refractive lens exchange
- Preoperative IOL calculation method (per CRF)
- Toric IOL calculation method (for toric IOLs only) (per CRF)
- Other surgical procedures during cataract or refractive lens exchange surgery (if applicable)

4.3 MEDICAL HISTORY AND CONCOMITANT MEDICATIONS

A targeted medical history (within 30 days prior to the date of surgery) will be collected for each patient in the study and includes the following: Diabetes, Hypertension, HIV Infection, Multiple Sclerosis, Rheumatoid Arthritis, Sjogren’s Syndrome, Atherosclerosis, Autoimmune disorder, Grave’s disease, Sarcoidosis, Sickle cell disease, and Ocular (specify). The number and percentage of patients with at least one medical condition and within each of the systemic medical histories will be reported in a table by toricity.

Two medical history and concomitant medication listings will be provided for all subjects/eyes. Both listings will include subject, study device, lens model (lens model OD/lens model OS), and the concomitant medication used to treat the medical history condition, when applicable. The systemic medical history listing will also include the targeted systemic medical history term (per the CRF). The ocular medical history listing will also include the ocular medical history term and the affected eye.

4.4 PREGNANCY

Women of childbearing potential are not excluded from participation. Women who gave birth after IOL implantation or who are pregnant or nursing at the time of enrollment are excluded from participation.

4.5 RETROSPECTIVE DATA

If available, retrospective data will be collected regarding the preoperative, operative, and immediate postoperative activities, and will be presented in tables, as described below.

4.5.1 Preoperative Biometry and Keratometry

Preoperative data that includes biometry and keratometry will be extracted from the chart review and presented separately for first implanted eye and second implanted eye (if applicable) and for all eyes by toricity. One table will include both biometry and keratometry data. Biometry data in the table includes axial length, ACD, lens thickness (if available), and white-to-white (if available); keratometry data in the table includes corneal cylinder [K2 (D) – K1 (D)].

Corneal curvatures (K1 and K2) reported in mm should be converted to diopter using the following equation.

Corneal curvature (diopter) = $337.5 \div \text{corneal curvature in (mm)}$

4.5.2 Preoperative Manifest Refraction and PRRE

Preoperative MRSE (defined as the sum of the sphere with half of the cylinder, reported value without taking the absolute value) and PRRE spherical equivalent will be summarized descriptively as a continuous variable (n, mean, median, standard deviation, minimum and maximum, and two-sided 95% CI for the mean) by toricity separately for first implanted eye and second implanted eye (if applicable) and for all eyes. For toric lenses, PRRE cylinder and axis will also be reported. PRRE cylinder should be converted to absolute values to allow for accurate analysis of plus and minus cylinder input from the CRF. Signs should be maintained for MRSE and PRRE.

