- Clinically Significant Requiring YAG: Clinically significant PCO adversely affecting subject's VA and requiring posterior capsulotomy.

For posterior capsulotomy assessment, indicate whether a posterior capsulotomy has been performed. If performed, report the date of the procedure.

If subjective PCO is graded as present, also record whether it is due to residual cataract (e.g., posterior subcapsular cataract).

7.3.13 *Tonometry*

Perform tonometry assessment in both eyes according to the Investigator's standard of care. Record IOP.

7.3.14 *Dilated Fundus Examination*

Dilated fundus examination includes ophthalmoscopic assessments of the vitreous, retina, macula, choroid, and optic nerve of both eyes. This assessment must be performed by medically qualified study staff.

7.3.15 *Actual Axis of IOL Orientation*

Post-operatively, examine each toric IOL via slit lamp subjectively and document the actual IOL orientation in degrees (0-180 degrees) of the IOL axis (designated by the 3 indentions on each side of the toric IOL optic). It is recommended that a slit lamp photograph be printed and kept in the source. Actual axis of orientation should be completed after dilation.

Post-operative Day 1 IOL orientation in degrees (0-180 degrees) of the IOL axis will be extracted from the chart review, if available.

7.3.18 *Adverse Events*

AEs are collected from the time of initial exposure to the study model IOL(s) and throughout the duration of the study. Any preexisting medical conditions or signs/symptoms present in a subject prior to exposure of the study model IOL(s) (i.e., before cataract surgery) are not considered AEs in the study and should be recorded in the Medical History section of the eCRF. See Section 9.2 and 9.3 for further details.

7.3.19 *Device Deficiencies*

Record any Device Deficiencies that are reported or observed since the time of initial exposure to the study model IOL(s). Requirements for reporting device deficiencies in the study can be found in Section 9.

7.4 *Retrospective Data Collection*

If available, retrospective data will be collected regarding the pre-operative, operative, and post-operative activities, as detailed in the sections below.

7.4.1 *Biometry and Keratometry*

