Details of pre-operative biometry performed as per the standard of care will be documented from the chart review including information regarding the biometer model. Keratometry details will also be documented. If more than one set of keratometry data are documented in the source data for one eye (e.g., values from different measurements or devices), select those used in the IOL power and model selection process for entry into the study database.

7.4.2 *Pre-Operative Manifest Refractive Error*

At the time of study entry, site staff will transfer preoperative sphere, cylinder, and axis for each eye to the study database (retrospective data collection based on the preoperative manifest refraction).

7.4.3 *IOL Calculation Method*

At the time of study entry, sites will indicate in database, which formula was used for IOL power calculation as per standard of care when available (retrospective data collection).

7.4.4 *Predicted Residual Refractive Error*

At the time of study entry, sites will document in the study database which residual refraction was expected after study model IOL implantation for both eyes when available. For toric IOLs, the predicted residual cylinder and corresponding axis should be extracted from the chart review, if available (retrospective data collection).

7.4.5 *Lens Model and Refractive Power*

At the time of study entry, the lens model and refractive power selected preoperatively as per standard of care will be indicated in the study database (retrospective data collection).

7.4.6 *Other Surgical Procedures During Cataract or Refractive Lens Exchange Surgery*

For any additional procedures that were performed in the context of cataract or refractive lens exchange surgery, such as placement of capsular tension devices or creation of arcuate corneal incisions, these are captured in the study database for better understanding of treatment outcomes. This also includes any limbal relaxing incision (LRI).

7.4.7 *Actual Axis of IOL Orientation*

If available, collect actual toric IOL orientation in degrees (0-180 degrees) of the IOL axis (designated by the 3 indentions on each side of the IOL optic) from the 1-day post-operative visit.

7.4.8 *Retrospective Post-operative Visual Acuity*

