9 SAMPLE SIZE AND POWER CALCULATIONS

The study will recruit a total of 210 subjects for both AcrySof PanOptix IOL models to obtain 200 evaluable subjects (n=100 non-toric and n=100 toric). A minimum of 100 subjects bilaterally implanted with AcrySof PanOptix non-Toric should be evaluable. In addition, a minimum of 100 subjects with at least one eye implanted with AcrySof PanOptix Toric should be evaluable. Alcon will attempt to enroll all variants in the AcrySof PanOptix Toric family. ISO 22979 and ISO 11979-7 recommend a sample size of n=100 for IOLs where safety and performance risks can be adequately addressed with the sample size required of a Level B clinical investigation. Therefore, a target enrollment of up to 105 (enrolled) to achieve a goal of 100 evaluable subjects for both AcrySof PanOptix toric and non-toric models is justified by ISO standards for IOLs. Based on a pooled standard deviation of 0.07 logMAR and a t-distributed error, a sample size of 100 subjects gives an expected half width of a 95% confidence interval of 0.014 logMAR. Thus, it can be expected with 95% confidence that the estimated mean binocular BCDVA will be within 0.014 logMAR (< 1 letter on a logMAR visual acuity chart) of the true mean with a sample size of at least 100 subjects and a standard deviation of 0.07 logMAR. Descriptive results from this long-term RWE study are sufficient to provide a comparison to shorter term follow-up data of these models, and SotA safety and performance thresholds. Performance and safety outcome measures will be stratified by models (toric and non-toric).

Table 2. Subject Sample Distributions

AcrySof PanOptix Family Implants	
Toric	100
Non-Toric	100

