10 STATISTICAL METHODS

10.1 STATISTICAL RULES

Appropriate descriptive statistics will be computed and presented for all categorical and continuous endpoints. For categorical variables, the number and percentage of subjects/eyes within each category of interest will be presented. The percentages will be calculated based on the respective analysis set or the number of non-missing observations (i.e., the number of patients/eyes assessed) in the respective analysis set where applicable. For categorical variables with at least one missing observation, a category of 'missing' will be added to document the number of missing

observations. If there is no missing observation, a category of ‘missing’ may not be added. Percentages will be rounded to one decimal place.

For continuous variables, the number of subjects/eyes with non-missing data, mean, standard deviation, median, minimum and maximum, and 95% CI of the mean, when applicable, will be calculated. There will be no imputation for missing data. Means and medians will be rounded to one decimal more than that with which the original data are recorded. The standard deviation will be rounded to two decimals more than the original data. Minimum and maximum values will be reported with the same number of decimals with which the original data are recorded.

Theoretical lower limits will be set for 95% CIs of the mean as follows:

- VA – -0.30
- IOP – 0.00
- Absolute Residual Cylinder – 0.00
- Misalignment – 0.0
- IOL Axis – 0.0

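### Toric axis output: predicted residual cylinder loses its sign without the axis being rotated, and, separately, the SAP foresees a linear mean and CI for IOL axis

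*SAP*

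**What the plan says.** **PRRE cylinder and axis.** SAP 4.5.2 summarises preoperative MRSE and PRRE spherical equivalent with n, mean, median, SD, range and a 95% CI. For toric eyes it adds: "For toric lenses, PRRE cylinder and axis will also be reported". The cylinder rule follows: "PRRE cylinder should be converted to absolute values to allow for accurate analysis of plus and minus cylinder input from the CRF". The paragraph ends: "Signs should be maintained for MRSE and PRRE". The source is Protocol 7.4.4, under which "the predicted residual cylinder and corresponding axis should be extracted from the chart review", where available. Neither document fixes a cylinder convention for these chart entries.

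**IOL axis.** This is a different variable. Under Protocol 7.3.15 the examiner is to "document the actual IOL orientation in degrees (0-180 degrees) of the IOL axis" at the slit lamp. For continuous variables in general, SAP 10.1 says that "mean, standard deviation, median, minimum and maximum, and 95% CI of the mean, when applicable, will be calculated". It then states: "Theoretical lower limits will be set for 95% CIs of the mean as follows". The list that follows includes IOL axis, with a limit of 0.0. PRRE axis is not on it.

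**The concern.** The sign of a cylinder and its axis form one quantity. If the sign is removed and the axis left alone, the information needed to read the axis is lost. SAP 4.5.2 expects both signs, so its rule meets its stated aim for magnitude but not for axis. The fault does not depend on averaging: a listing, a median or a range would carry it too.

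For IOL axis, a limit on the CI of a mean is needed only if a mean and CI are to be computed. Orientation repeats every 180 degrees, so 0 and 180 are the same meridian and an ordinary mean can point to the wrong one.

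Toric subjects make up 100 of the 200 planned evaluable subjects, and results are stratified by toricity. At stake is whether the descriptive axis output for that half of the study can be read correctly.

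**Working it through.** The documents state no axis figure to reproduce. All axis and refraction values below are illustrations.

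**1. Absolute cylinder with an unrotated axis**

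The power-vector form of sphere S, cylinder C, axis A is M = S + C/2, J0 = −(C/2)·cos 2A, J45 = −(C/2)·sin 2A.

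| Form | M (D) | J0 (D) | J45 (D) |
|---|---|---|---|
| As entered: +0.25 −0.50 × 180 | 0.00 | +0.25 | 0.00 |
| Transposed: −0.25 +0.50 × 90 | 0.00 | +0.25 | 0.00 |
| Sign dropped, axis kept, read as plus cylinder: 0.50 × 180 | 0.00 | −0.25 | 0.00 |

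- The first two rows are the same refraction. The third is 90 degrees away.
- J0 differs by 0.50 D, which is 2 × 0.50 = 1.00 D of cylinder, or twice the cylinder itself.
- The magnitude stays 0.50 D. The spherical equivalent does not change under transposition, because (S + C) + (−C)/2 = S + C/2.

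The share of eyes affected equals the share entered in the minority convention, which the documents do not give. If every site uses one convention, the share is zero.

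Simulation of 100 toric eyes (assumed true plus-cylinder axis 90, assumed axis SD 10 degrees), with minus-cylinder entries left unrotated:

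| Share entered as minus cylinder | Mean axis | SD of axis |
|---|---|---|
| 0% | about 90 | 10 |
| 25% | about 90 | 42 |
| 50% | about 90 | 59 |

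The recorded spread then mostly reflects data-entry convention. These SDs show the size of the mixing; the SAP does not say that an SD of PRRE axis will be produced.

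**2. Linear mean of IOL axis**

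Take lenses at 2, 5, 175 and 178 degrees, all within 5 degrees of horizontal.

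- Arithmetic mean: (2 + 5 + 175 + 178)/4 = 90, which is vertical.
- SD: √[(88² + 85² + 85² + 88²)/3] = √(29,938/3) = 99.9.
- 95% CI: −69.0 to 249.0, with the lower end then set to 0.
- Double-angle mean: the doubled angles are 4, 10, 350 and 356. Their sines cancel and their cosines are positive, so the mean direction is 0, that is, axis 0/180.

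Simulation at n = 100 (assumed true axis 0/180, assumed SD 10 degrees): mean about 90, SD about 82, 95% CI about 74 to 106. The interval looks precise but is centred on the wrong meridian.

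The limit at 0 never took effect at n = 100 in any scenario; CI lower ends averaged about 73 to 88. The fault lies in the linear mean.

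**3. Misalignment, if differenced linearly**

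An intended axis of 178 and an achieved axis of 2 differ by 176 as raw numbers, but by min(176, 180 − 176) = 4 degrees as orientations.

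**The case against.** Four stronger readings are tempting, and the documents do not support them.

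- **Biased spherical equivalent.** A reader might infer that the absolute cylinder feeds PRRE spherical equivalent. SAP 4.5.2 points the other way. It defines MRSE without an absolute value, limits the absolute value to PRRE cylinder, and then says "Signs should be maintained for MRSE and PRRE". The natural reading is a signed spherical equivalent beside an unsigned cylinder magnitude. At most, PRRE in that sentence needs the words spherical equivalent added.
- **PRRE axis will be averaged.** SAP 4.5.2 attaches mean, SD and CI to MRSE and PRRE spherical equivalent. Axis is only to be reported, with no statistic named. The opening of SAP Section 4 lists PRRE as cylinder and spherical equivalent, without axis.
- **The limit at 0 distorts the result.** Zero is the lower end of the recorded scale, and the limit does not take effect at the planned sample size.
- **IOL-axis and misalignment results are certainly wrong.** The public SAP runs from 5.3.1 straight to 6.2, although its contents put 5.3.1 on page 14 and Section 6 on page 19. The detailed IOL-axis text may lie in between and may use a circular method. SAP 10.1 also gives means and CIs only when applicable.

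It is also fair to say that PRRE is collected only where available, that the four-lens example was chosen to straddle 0/180, and that axes far from 0/180 average without trouble.

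Two things stand after all this. SAP 4.5.2 anticipates mixed signs, reports axis and has no rotation rule in the visible text. SAP 10.1 names IOL axis among variables given a CI of the mean; if a circular method exists elsewhere, 10.1 conflicts with it and still needs correcting.

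**Conclusion.** Both faults hold, and both are minor. They are separate, because IOL axis is read from marks on the lens and has no cylinder sign.

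1. PRRE axis will be 90 degrees off, relative to the other eyes, for every eye entered in the opposite convention. This assumes that conventions are in fact mixed, as SAP 4.5.2 anticipates. Cylinder magnitude and spherical equivalent are correct as planned.
2. A linear mean and CI for IOL axis, as implied by SAP 10.1, can name the wrong meridian when lenses lie near 0/180. This is a strong inference, subject to the text that is not public.

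No hypothesis is tested. Binocular BCDVA and the adverse event tables do not use axis and are untouched.

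**What to change.** **PRRE (SAP 4.5.2)**

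- Compute spherical equivalent from the signed values first.
- Then transpose every entry to one convention before reporting cylinder and axis. For cyl < 0: S′ = S + cyl, cyl′ = −cyl, axis′ = axis ± 90 modulo 180.
- State that the instruction to keep signs refers to spherical equivalent.

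**IOL axis (SAP 10.1)**

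- Delete IOL axis from the list of CI lower limits.
- Report it by listing, by orientation category, or with double-angle statistics. Any of the three avoids the problem.
- If the non-public text does not already do so, define misalignment as the smallest angle modulo 180, that is min(|d|, 180 − |d|).

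The cost is a few lines of SAP wording and a short derivation in the analysis dataset. No new data are needed, but the cylinder sign as entered must be kept in the raw data until the transposition is done.
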